9.2.2. Outcome measures

The following outcome measures are assessed post-discharge, and will be measured during the variable post-index period starting on the treatment index date for the apixaban and warfarin cohorts.

Treatment patterns

- Persistent days (mean, SD, median, IQR, min, max) will be reported for patients until they discontinue, switch or end of follow-up based on definitions below
- Patients discontinuing outpatient treatment of apixaban or warfarin, respectively (NDC codes from LRx; n, %)

Note: Discontinuation will be defined as the occurrence of a ≥ 30 day gap from the run-out of days' supply of the treatment (post-discharge) index prescription (i.e. apixaban or warfarin) to the date of the next claim for the respective therapy or with no other claims for the respective therapy. The date of the discontinuation will be defined as the last day of the days' supply of the last filled prescription.

- Time (in days) from treatment index date to discontinuation date (mean, SD, median, IQR, min, max)

Note: Kaplan-Meier (KM) curves will be generated to measure median time (and 95 % CI) to discontinuation.

- Patients switching to an OAC other than apixaban or warfarin, respectively (switched) (NDC codes from LRx; n, %)

Note: Patients will be considered to have switched if they filled a prescription for OAC other than apixaban or warfarin, respectively (identified through NDC codes in LRx) or for PAC within 30 days before or after the run out date of index treatment. The date of the switch will be defined as date of the prescription of such a therapy (OAC or PAC).

- Time (in days) from treatment index date to switch date, defined as the date of the first claim for the new OAC or PAC (mean, SD, median, IQR, min, max)

Note: KM curves will be generated to measure median time (and 95 % CI) to switching

Clinical Outcomes

The following clinical outcomes will be assessed during the time patients are persistent with their respective index apixaban or warfarin treatment (treatment index):

- Patients with ≥ 1 hospitalization for recurrent VTE (ICD-10 codes in CDM; n, %)
- Incidence rate (IR) of recurrent VTE (per 100 patient years)
 - The date of the first observed event will be flagged. The numerator for IR will be the number of patients with the event of interest and denominator will be the ‘at risk’ period i.e. the time to first event. The 95% confidence intervals (CI) will also be reported.

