Note: Recurrent VTE will be defined as inpatient hospitalization with a primary diagnosis of VTE occurring 7 or more days after the first hospitalization discharge date.

- Time (days) from first hospitalization discharge date to first recurrent VTE hospitalization (mean, SD, median, IQR, min, max)
- Time (days) from treatment index date to first recurrent VTE hospitalization (mean, SD, median, IQR, min, max)
- Patients with ≥ 1 hospitalization for major bleeding (ICD-10 codes in CDM; n, %)
- IR of major bleeding (per 100 patient years)

Note: Major bleeding will be defined as inpatient hospitalization with primary diagnosis of gastro-intestinal bleeding, intracranial hemorrhage (ICH) or other major bleeding

- Time (days) from first hospitalization discharge date to first major bleeding episode (mean, SD, median, IQR, min, max)
- Time (days) from treatment index date to first major bleeding episode (mean, SD, median, IQR, min, max)
- Patients with ≥ 1 CRNM bleeding event (n, %)
- IR of CRNM bleeding (per 100 patient years)

Note: CRNM bleeding will be defined as inpatient hospitalization with a secondary diagnosis code for bleeding (without a major bleeding code in the primary position) or an outpatient encounter with a diagnosis code in any position for CRNM GI bleeding or other non-critical types of bleeding. Specifically, it is defined as:

(1) An inpatient admission with a secondary diagnosis for “noncritical site” bleeding such as GI bleeding or other selected noncritical types/sites of bleeding (excluded if major bleeding occurred during the same hospitalization), OR

(2) An outpatient encounter with a diagnosis code for GI bleeding and other selected noncritical types/sites of bleeding.

Any CRNM bleeding events (as described above) that follow a major bleeding event (described above) will not be included in the analysis of CRNM bleeding

- Time (days) from first hospitalization discharge date to first CRNM bleeding episode (mean, SD, median, IQR, min, max)
- Time (days) from treatment index date to first CRNM bleeding episode (mean, SD, median, IQR, min, max)

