9.6. Data analysis

Descriptive statistics will be produced for all relevant study measures previously described, for the overall cohort and for each treatment (apixaban and warfarin). Categorical measures will be presented using frequency (number of patients [n]) and percentage (%) of total study patients observed in each category. Continuous and count variables will be presented as the mean, SD, median, minimum, maximum and IQR. As relevant, continuous variables will also be categorized into intervals. Univariate statistics will be calculated for each measure of interest. No comparisons will be made between the two cohorts..

Four multivariable regression models will be developed for this study. Cox proportional hazards models will be conducted to evaluate both the risk (expressed as hazard ratios with corresponding 95% confidence intervals) of discontinuing or switching from the index treatment as well as the risk of experiencing a clinical event (i.e., recurrent VTE, major bleeding, or CRNM bleeding).. The main effect variable will be the treatment cohort (apixaban vs. warfarin, with warfarin as the reference group). Covariates to be considered for inclusion into the models will include demographic and clinical characteristics of interest. A backward elimination of independent variables least associated with the dependent variable may be used. Clinically relevant covariates that are not retained during backward elimination may also be forced into the model. Collinearity among the variables of interest will be evaluated during model development.

Kaplan-Meier analyses will also be utilized to report the time to an event of interest (e.g., switch, discontinuation). Kaplan-Meier is a method for estimating the probability of the proportion of individuals remaining in the sample at a particular time from an initiation point. It takes into account patients lost or censored before the study endpoint. All analyses will be based on observed, not projected, data. Analyses will be conducted using SAS[®] Release 9.4 (SAS Institute Inc., Cary, NC), and the results will be reported in Excel tables.

Any major modifications of primary endpoint definitions (treatment patterns) or their analyses would be reflected in a protocol amendment.

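### The outpatient part of the CRNM bleeding endpoint depends on how often patients are seen; if warfarin patients have more captured encounters, the planned apixaban-versus-warfarin hazard ratio would tilt towards apixaban, and the plan neither measures nor handles this.

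*Combined protocol and SAP*

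**What the plan says.** The CRNM note in section 9.2.2 defines the outpatient limb twice. The summary sentence admits "an outpatient encounter with a diagnosis code in any position for CRNM GI bleeding or other non-critical types of bleeding". The numbered definition that follows admits "An outpatient encounter with a diagnosis code for GI bleeding and other selected noncritical types/sites of bleeding". Neither asks for a particular encounter type, a reason for the visit, a second claim or any treatment of the bleed. The first such event is used: "The date of the first observed event will be flagged". Follow-up is on treatment: "The following clinical outcomes will be assessed during the time patients are persistent with their respective index apixaban or warfarin treatment".

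The neighbouring endpoint is much tighter: "Major bleeding will be defined as inpatient hospitalization with primary diagnosis of gastro-intestinal bleeding, intracranial hemorrhage (ICH) or other major bleeding". Recurrent VTE also needs an inpatient stay with a primary diagnosis.

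Section 9.6 plans Cox models for "the risk of experiencing a clinical event (i.e., recurrent VTE, major bleeding, or CRNM bleeding" and adds: "The main effect variable will be the treatment cohort (apixaban vs. warfarin, with warfarin as the reference group". On adjustment it says: "Covariates to be considered for inclusion into the models will include demographic and clinical characteristics of interest". The baseline measures in section 9.2.1 contain no count of encounters. Section 9.8 acknowledges miscoding, under-coding and care at sites that do not contribute data. It does not mention detection that differs between the cohorts.

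**The concern.** A minor bleed that sends the patient to a doctor is recorded whatever the drug. A minor bleed that does not is recorded only if the patient is seen for something else soon afterwards and the bleed is then coded, perhaps as a secondary diagnosis. For the second kind, the chance of entering the endpoint rises with the number of encounters that the databases capture.

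If one cohort has more captured encounters during follow-up, its recorded CRNM rate rises without any difference in bleeding. Warfarin is the natural candidate, because anticoagulation monitoring brings patients into contact with care, so the distortion would favour apixaban, the product under study. It would affect both the incidence rates and the hazard ratio. Adjustment for baseline characteristics cannot remove it, because the difference in detection arises after the treatment index date. A large sample narrows the interval around the distorted value without moving it.

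**Working it through.** The documents give no visit rate, bleeding rate, event count or power figure, so there is no planned number to reproduce. The check asks what hazard ratio the endpoint would return if true bleeding were identical.

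**Assumed inputs (none from the documents)**
- f: share of codeable CRNM bleeds recorded only if another encounter falls near them; 0.3 or 0.6. Inpatient bleeds and bleeds that prompt their own visit belong to the remaining 1 - f.
- v: captured outpatient encounters per year; 6-8 on apixaban, 12-20 on warfarin.
- w: period after the bleed in which an encounter would still lead to a code; 2-4 weeks.

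**Formulas**
- Detection of a visit-dependent bleed: p = 1 - exp(-v × w/52), with w in weeks.
- Apparent hazard ratio at a true value of 1: HR = [(1 - f) + f × p_apixaban] / [(1 - f) + f × p_warfarin].

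| Encounters/year (apixaban / warfarin) | Window | p apixaban | p warfarin | HR, f = 0.3 | HR, f = 0.6 |
|---|---|---|---|---|---|
| 8 / 12 | 2 weeks | 0.265 | 0.370 | 0.96 | 0.90 |
| 8 / 12 | 4 weeks | 0.460 | 0.603 | 0.95 | 0.89 |
| 6 / 12 | 2 weeks | 0.206 | 0.370 | 0.94 | 0.84 |
| 6 / 12 | 4 weeks | 0.370 | 0.603 | 0.92 | 0.82 |
| 8 / 20 | 2 weeks | 0.265 | 0.537 | 0.91 | 0.77 |
| 8 / 20 | 4 weeks | 0.460 | 0.785 | 0.90 | 0.78 |
| 6 / 20 | 2 weeks | 0.206 | 0.537 | 0.88 | 0.73 |
| 6 / 20 | 4 weeks | 0.370 | 0.785 | 0.87 | 0.71 |

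The last row at f = 0.6 in full: (0.4 + 0.6 × 0.370) / (0.4 + 0.6 × 0.785) = 0.622 / 0.871 = 0.71. The ranges are therefore 0.87-0.96 at f = 0.3 and 0.71-0.90 at f = 0.6. With equal v in both cohorts, or f = 0, the formula gives exactly 1.00.

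**Timing.** A simulation with true HR 1 took f = 0.5, a 30-day window, 180 days of follow-up and 6 encounters a year on apixaban. Warfarin had extra encounters at 26 a year to day 30, 12 a year to day 90 and 6 a year after that. The ratio of recorded events was 0.82 overall, 0.76 for bleeds in the first 30 days and 0.86 from day 90. If extra encounters are concentrated early, the distortion also varies over time.

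**Would it show as a finding?** The feasibility counts in section 9.4, taken before eligibility criteria and linkage, give an apixaban share of 53,918 / (53,918 + 18,035) = 0.749. By Schoenfeld's formula (two-sided 0.05, 80% power), events = (1.96 + 0.842)² / [0.749 × 0.251 × (ln HR)²]. That gives about 1,204 events for a spurious HR of 0.83 and 4,699 for 0.91. With 1,000 events, the chance of a significant result would be 72% and 25% respectively.

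**The case against.** The strongest objection is that the decisive premise is not documented. The protocol does not mention warfarin monitoring or its frequency, or say whether such contacts appear in the Dx claims or the participating CDM hospitals. Even if they do appear, a bleeding diagnosis must be coded there, for a bleed not otherwise recorded. The list of CRNM codes is not shown either, so the share f cannot be estimated. This stands. A reader might infer that the planned hazard ratio is biased towards apixaban. The documents support only that it could be, with a size anywhere from nil to large.

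It can also be said that CRNM bleeding belongs to a secondary objective, that major bleeding is reported beside it on a definition much less exposed to visit frequency, and that section 9.8 limits results to association. All of this is true and lowers the stakes, but none of it shows whether a CRNM hazard ratio below 1 reflects bleeding or visits. Section 9.6 also disclaims comparison of the two cohorts. That does not dispose of the point, because a hazard ratio with cohort as main effect is such a comparison, and the two statements need reconciling.

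Finally, stronger remedies are tempting and would overreach. Replacing the CRNM definition outright would rest on an unverified premise. Deleting codes from visits made only for monitoring has no working definition. It would fall almost entirely on warfarin, and could remove genuine bleeds and bias the result the other way.

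**Conclusion.** The concern holds in conditional form. From the text alone, the outpatient limb of CRNM bleeding depends on encounters, a between-drug hazard ratio is fitted to it, and encounter frequency is neither measured, handled nor named as a limitation. The direction, towards apixaban, follows only if warfarin patients have more captured encounters. On the assumptions shown, the hazard ratio under equal bleeding is 0.87-0.96 with 30% of bleeds visit-dependent and 0.71-0.90 with 60%. It is 1.00 if encounter rates are equal or every bleed prompts its own visit. These figures illustrate the mechanism and do not estimate the bias in this study. The point concerns the outpatient limb; the inpatient limb, major bleeding and recurrent VTE need a hospitalization and are much less exposed. It is a cheap improvement worth making before the analysis is run.

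**What to change.** Keep the protocol's CRNM definition and make four additions.

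1. **Section 9.2.2.** Split CRNM events into (a) inpatient secondary-code bleeds, emergency room encounters, and outpatient encounters with the bleeding code in primary position; and (b) all other outpatient encounters, office or hospital-based, with the code only in a non-primary position. Hospital outpatient visits must not pass into (a) merely because they come from CDM.
2. **Section 9.6, models.** Pre-specify a CRNM Cox model for time to first component (a) event, without censoring at an earlier component (b) event, alongside the all-component model. Treat the all-component hazard ratio as a drug difference only if the two agree, and state in advance what counts as agreement. Amend the stated number of models and reconcile the disclaimer of comparisons with the cohort main effect.
3. **Section 9.6, description.** Report outpatient encounters per person-time by cohort. This tests the premise directly. Do not simply add post-index visits as a covariate, since treatment and bleeding both affect them.
4. **Section 9.8.** Name differential detection of outpatient CRNM bleeding as a limitation.

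Do not delete codes from visits judged to be for monitoring only. The protocol describes CDM as covering outpatient and emergency room services and Dx as holding diagnoses and location of care, so no new data source should be needed; that code position is usable in both should be confirmed. The cost is a few lines of text and one extra model, with fewer events and a wider interval for component (a).

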9.3. Data sources

IQVIA's CDM database will be linked to Dx and LRx for this analysis.

Hospital Charge Data Master (CDM)

IQVIA's Hospital CDM is comprised of hospital-based data which are sourced from hospital CDM files that roll up to the UB-04 files which are submitted for payment. Data covers non-federal, acute-care short-stay hospitals, covering inpatient and outpatient services, including emergency room (ER) utilization with information on diagnoses, procedures, treatment and daily un-adjudicated charge details. Limited patient and hospital characteristics are also available. Data is available from 2001, with a data lag of approximately 6 weeks. The data cover more than 450 hospitals per month and approximately 8 million inpatient visits and 105 million outpatient visits per year. Charge details during a stay are provided on a daily basis (and lack a time stamp). Diagnoses lack a time or day stamp.

It is important to note some limitations of this dataset. Firstly, because this is an open-source database, there is a loss of visibility to healthcare activity and consumption outside of hospitals that participate in/contribute to the database. Secondly, unlike administrative health plan claims data, it is not possible to apply continuous enrollment (CE) requirements. Proxies for CE must be implemented based on hospital reporting to provide greater assurance that patient healthcare activity within this database is captured during the study period. Socioeconomic details, such as race/ethnicity or income, are unavailable in the data. Clinical detail is also limited. Due to patient privacy reasons, a subject who is 85 years or older will only have the recorded age of "85". And finally, only charges are available in CDM, thus a national cost to charge ratio must be applied to charges.

Medical claims (Dx) database

IQVIA's Dx database captures over one billion pre-adjudicated claims and three billion records obtained annually from approximately 800,000 office-based physicians and specialists. Dx database is updated on a weekly basis with approximately a 30-60 day lag for data completeness. Key information includes International Classification of Diseases, ninth revision, clinical modification (ICD-9-CM) and International Classification of Diseases, tenth revision, clinical modification (ICD-10-CM) diagnoses, CPT/procedure/Healthcare Common Procedure Coding System (HCPCS) for medical conditions and procedures, date of service, location of care, (pre-adjudicated) charged amount for service, payer types (commercial, Medicaid, Medicare, cash payment), patient age and sex. Note that inpatient data is limited.

Longitudinal Prescription Claims (LRx)

IQVIA LRx database captures information on dispensed prescriptions sourced from retail, mail, long-term care, and specialty pharmacies. These suppliers have direct, long-standing relationships with IQVIA, with many providing data on a daily basis, and all suppliers support weekly data feeds with an ability to provide insight within ten days of the end of each week. This enables IQVIA to ensure that the LRx database has good longitudinal, representative, and current data from consistent and stable suppliers. IQVIA has industry-leading coverage in the following channels: 92% coverage of the retail channel, 72% coverage of standard mail service, and 76% of long-term care facilities. IQVIA receives specialty data directly from the pharmacy resulting in near census data coverage, contributing to greater precision for longitudinal analysis. Additionally, diagnosis is included directly on the majority of specialty pharmacy transactions from the specialty pharmacy providers. An important strength of the LRx database for this analysis is the longitudinal capture of adjudicated and cash prescriptions for all age categories, regardless of insurance type.

Linkage Methodology

A proposed dataset will be constructed utilizing patient data from LRx, Dx and CDM, with the appropriate dataset being selected based upon proportion of linked patients. This process which is compliant with The Health Insurance Portability and Accountability Act of 1996 (HIPAA) is described below:

- IQVIA has developed a patented and proprietary encryption algorithm that utilizes actual patient-level information to create a unique Patient identifier (ID)⁸
 - First Name
 - Last Name
 - Date of Birth
 - Gender
 - Street Address
 - ZIP Code (5-digit)
- IQVIA deploys this encryption tool across its data suppliers to de-identify patient data at the source
- Once IQVIA brings the encrypted and de-identified data in house, the data undergoes a deterministic matching process to be assigned a unique and persistent IQVIA patient ID; we are then able to match the Patient ID across our portfolio of databases

It is important to note that IQVIA uses a deterministic matching algorithm to link patients across databases.⁹ This type of algorithm uses actual patient information, rather than statistical probability based on patient age, number of visits, etc. to ensure continuity of patient records across datasets. Source data is passed through an encryption engine and a one-way hash algorithm results in “tokens” that cannot be decrypted. The resulting output is de-identified patient records that can be linked to other assets in the IQVIA patient data warehouse. Patient Tokens as well as other attributes (e.g., gender) are used for matching to the IQVIA Patient Master to assign an existing or new IQVIA Patient ID which can be used as available across data sources. The IQVIA matching algorithm achieves a balance between false positives

(~2%) and false negative (~3%) rates, optimizing the size of the linked sample that can be obtained.

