9.2. Variables

[figure not shown]
From the final sample, the following measures will be reported (Figure 2):

1. Patients with a claim for the respective treatment (apixaban for apixaban cohort or warfarin for warfarin cohort; using NDC from LRx) as their first post-discharge outpatient treatment (on or within 30 days following discharge i.e. discharge date or ≤ 30 days after discharge date) (n, %). These patients will comprise the analytic cohort for outcomes assessment.

- a. The date of the first post-discharge outpatient prescription claim in LRx (apixaban or warfarin) will be defined as the ‘treatment index date’ for patients in both cohorts respectively.
 - b. Patients will be required to have pharmacy stability during the 6-month period preceding the treatment index date, defined as consistent reporting of data in each month from the pharmacy associated with the treatment index date in LRx to ensure continuous visibility within LRx. The number of patients excluded due to lack of stability will be reported (n, %)
 - c. Patients with recurrent VTE, major bleeding, or CRNM bleeding between the discharge date and the treatment index date will be excluded. The number of patients excluded due to these reasons will be reported (n, %).
 - d. Patients will be followed from the treatment index date until the earliest of last prescription, last patient medical claim, end of pharmacy stability, or end of study period using the Dx/Rx databases.
2. Patients with OAC (warfarin, apixaban, rivaroxaban, dabigatran, or edoxaban) other than the respective inpatient treatment as their first outpatient prescription claim (on discharge date or within 30 days of discharge) (NDC codes from LRx; n, %). These patients will be captured as having switched from inpatient therapy and will not be further evaluated for outcomes.
 3. Patients with no post-discharge outpatient prescription claim for any OAC (on or within 30 days of discharge) (NDC from LRx; n, %)

All study outcomes will be evaluated for the apixaban and warfarin cohorts.

Figure 2. Study Flow

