9.8. Limitations of the research methods

This study will have limitations inherent to observational studies involving claims and hospital charge data, as well as limitations related to the study design. Results from retrospective studies must be interpreted with caution and can only establish associations and not cause-and-effect relationships.

Claims data do not provide as much clinical detail as medical records as they are primarily collected for the purposes of payment. Therefore, there is a potential for miscoding or misclassification (e.g., identification of newly treated VTE patients). There is also the potential for under-coding if they are not captured for billing purposes.

Because these are open-source databases, there is a loss of visibility to healthcare activity/consumption at pharmacies, offices and hospitals that do not participate/contribute to the databases. Pharmacy stability requirements will be applied to the index prescription pharmacy at the patient level. Nevertheless, LRx has high prescription coverage (e.g., 63% of retail pharmacies in the US). Over-the-counter products will not be captured.

Unlike administrative health plan claims data, it is not possible to define periods of continuous enrollment (CE). Only proxies can be implemented based on patient activity and pharmacy stability to provide greater assurance that patient healthcare activity within these databases is captured during the study period. The data also lack information on mortality.

Only patients with a hospitalization or outpatient visit to a hospital in the CDM database are present in the CDM database, therefore potentially representing a more severe population.

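### No hospital-reporting rule ends follow-up for recurrent VTE and major bleeding, which are seen only in CDM, so their rates are biased downward by an unknown amount

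*Combined protocol and SAP*

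**What the plan says.** **Events.** Section 9.2.2 takes both outcomes from CDM: "Patients with ≥ 1 hospitalization for recurrent VTE (ICD-10 codes in CDM; n" and, in the same form, "Patients with ≥ 1 hospitalization for major bleeding (ICD-10 codes in CDM; n". Each is an inpatient stay with the relevant primary diagnosis. For the incidence rate, the "denominator will be the ‘at risk’ period i.e. the time to first event", counted while the patient is persistent on index therapy.

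**Follow-up.** Section 9.2, item 1d, ends follow-up at the "earliest of last prescription, last patient medical claim, end of pharmacy stability, or end of study period using the Dx/Rx databases". Item 1b requires month-by-month reporting by the index pharmacy in LRx. Inclusion criteria 5 and 6 (Section 9.1.1) require activity in Dx and LRx before admission and after discharge. None of these refers to CDM reporting.

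**What the protocol says about CDM.** Section 9.3 warns that "there is a loss of visibility to healthcare activity and consumption outside of hospitals that participate in/contribute to the database", that continuous enrolment cannot be applied, and that "Proxies for CE must be implemented based on hospital reporting to provide greater assurance that patient healthcare activity within this database is captured". Section 9.8 describes the proxies differently: "Only proxies can be implemented based on patient activity and pharmacy stability".

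**The concern.** The numerator of each rate needs CDM to be reporting, and the denominator does not. Suppose the index hospital stops contributing in month 3 while the patient goes on filling the index drug and visiting an office until month 18. The plan credits 18 − 3 = 15 months of event-free time during which a readmission to that hospital would leave no trace.

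The plan already accepts the principle for the pharmacy side: it requires stable reporting by the index pharmacy and censors when that ends. It does not extend the principle to the database that supplies two of the three clinical outcomes in objective 3. The planned 95% confidence intervals describe sampling error only and would give no sign of the problem.

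**Working it through.** The protocol states no expected rate, event count or power for these outcomes, so there is no design figure to reproduce. The check is of direction and form.

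**Inputs.** None of these is given in the documents; all are assumptions.
- *v*: share of at-risk person-time in which the patient's index hospital is reporting to CDM.
- *c*: share of relevant admissions in that time that go to any reporting CDM hospital.
- *d*: share of relevant admissions that are still seen, at other CDM hospitals, after the index hospital stops reporting.
- True rate: 4 per 100 patient-years.

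**Formulas, for rare first events.**
- Plan as written: observed rate ≈ true rate × [*v* × *c* + (1 − *v*) × *d*].
- Follow-up censored at the end of index-hospital reporting: observed rate ≈ true rate × *c*.

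Whenever *v* < 1 and *d* < *c*, the first is smaller than the second. With *d* = 0 (worst case) their ratio is *v*. With *d* = *c* (nothing lost when the index hospital drops out) the ratio is 1.

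**Numbers, with c = 0.8 and the worst case d = 0.**

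| v | Plan as written: 4 × v × 0.8 | With reporting censor: 4 × 0.8 |
|---|---|---|
| 1.0 | 3.20 | 3.20 |
| 0.9 | 2.88 | 3.20 |
| 0.75 | 2.40 | 3.20 |
| 0.5 | 1.60 | 3.20 |

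For *v* = 0.75 the plan's rate thus lies between 2.40 (*d* = 0) and 3.20 (*d* = *c*).

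**Simulation check.** 400,000 patients were given Dx/LRx follow-up uniform on 0.1 to 2 years and a true rate of 4 per 100 patient-years; 40% lost hospital reporting at a uniformly distributed point of their follow-up, *c* = 0.8 and *d* = 0. This gave *v* = 0.80. The plan's rate was 2.58 (formula: 4 × 0.80 × 0.8 = 2.56); the censored rate was 3.23 (formula: 3.20). With about 400,000 × 1.05 × 0.0258 ≈ 10,800 events, simulation error is about 1/√10,800 ≈ 1%, so the agreement is good.

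**What censoring does not repair.** The factor *c* remains: 3.20 is still below 4, because admissions to non-CDM hospitals are never seen. Censoring also corrects the rate rather than the crude percentage, since events during unreported time stay unseen while the patient stays in the denominator.

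**Hazard ratios.** If the capture factor is the same in both cohorts it cancels, and the hazard ratio is roughly unchanged for rare events. If the factors are k_A and k_W, the estimate is multiplied by about k_A/k_W.

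**The case against.** **Disclosure.** Sections 9.3 and 9.8 both admit loss of visibility at hospitals that do not contribute. This stands for leakage to non-CDM hospitals, which is a property of the source and cannot be designed away. It does not cover the reporting gap: nowhere does the protocol say that unobserved time enters the denominator or that the rates are too low.

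**Generic text.** The statement that proxies must be implemented may be standard database description. The same paragraph says a cost-to-charge ratio must be applied, although this study has no cost outcome. That weakens any charge of a broken commitment. It does not remove the mismatch, which follows from item 1d and the outcome definitions alone.

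**Other CDM hospitals.** CDM covers more than 450 hospitals a month, linked by a persistent patient ID, so the data do not go dark when one hospital stops. This is right. It is why *d* appears above and why the present analysis should be kept beside the new one.

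**Dx as back-up.** These outcomes are specified from CDM, and Section 9.3 itself says that inpatient data in Dx are limited.

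**Stronger readings that the documents do not support.**
- A reader might derive a capture rate from 139,061 CDM patients over 5.66 years, about 24,560 a year, against more than 330,000 US admissions: about 7%. This compares patients with admissions and primary diagnoses with an unspecified position. It also ignores that every study patient has already used a CDM hospital. Other figures in the protocol give a different share: 8 million CDM inpatient visits × 7.0 to 8.4 per 1,000 = 56,000 to 67,200, or 17% to 20% of 330,000. Neither estimates the capture of a recurrence.
- A reader might conclude that all objective 3 rates are too low. CRNM bleeding also counts outpatient encounters. A major bleed missed in CDM would also fail to remove later CRNM events, which pushes that count up.
- A reader might conclude that the hazard ratios are biased. Nothing in the documents shows that capture differs by cohort.

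**Conclusion.** The point holds for the incidence rates and n (%) of recurrent VTE and major bleeding. Following the plan as written keeps person-time after the index hospital has stopped reporting, and this mechanism can only lower those figures.

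The size is unknown. It depends on how much person-time falls after reporting ends and on how many of those admissions are still seen at other CDM hospitals, and the documents give neither. If no index hospital stops reporting, this part of the bias is nil. In the assumed examples with *v* from 0.9 to 0.5 it is at most 10% to 50% of the rate that censoring would give.

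This should be fixed before the analysis, but it does not threaten the study's main aim. Objective 3 is secondary, and the treatment-pattern endpoints that Section 9.6 calls primary come from LRx and are unaffected.

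**What to change.** - **Section 9.2, item 1d:** for recurrent VTE and major bleeding, add the last month of continuous CDM reporting by the index hospital to the censoring dates.
- **Eligibility for these two outcomes:** require the index hospital to report to CDM in the month after discharge. Report the number of patients excluded and the person-time lost, by cohort.
- **Sensitivity analysis:** show the analysis under item 1d as now written beside the new one, so that events seen at other CDM hospitals are not lost.
- **Crude n (%):** give it with the observed follow-up, since censoring does not correct it.
- **Section 9.8:** state that both rates are minimum estimates because admissions to non-CDM hospitals remain unseen, and bring the list of proxies into line with Section 9.3.

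**Cost.** One reporting flag and one extra censoring date, with some loss of patients, person-time and precision. Monthly reporting status by hospital must be available. Section 9.3 presupposes this but does not state it, so it should be confirmed first.
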